#### 20.3.5 Adherence and Retention Analyses

Adherence to the protocol will be assessed with a smartphone-assisted medication adherence platform [94] in which the subject takes a video of drug administration at each dose, and transmits this to study personnel.

This program has been used successfully in previous studies, and includes security provisions that ensure protection of confidentiality and privacy. If the participant is unable to use the smartphone-assisted platform then medication adherence will be ensured using pill counting and meeting with the study nurse practitioner

Number of participants that complete the treatment phase of the study (through T8), complete the follow-up phase of the study (through T10), and are lost to follow-up will be collected. Frequency of and reasons for discontinuation of the intervention or study follow-up will also be tallied.

### 20.3.6 Baseline Descriptive Statistics

Treatment groups will be compared on several baseline characteristics, including sex, age, race/ethnicity, education level, baseline measures of alcohol consumption (% drinking days and % heavy drinking days), alcohol craving (PACS), anxiety (BAI), mood (BDI-II), CAPS total, and self-efficacy (AASE). Categorical data will be tallied, and means and standard deviations of continuous scores will be calculated.

### 20.3.7 Planned Interim Analysis

### 20.3.7.1 Safety Review

The DSMB will meet (in person or by teleconference) at least annually, including prior to enrollment of the first participant, following completion of treatment of the first 5 completers, after completion of treatment of the first 20 completers, and upon completion of enrollment for the trial. Prior to each meeting, the PI will prepare a report to the Board including review of the aggregate analysis of adverse events/serious adverse events.

Following each meeting, the board will provide the PI with a report including a recommendation to continue the study unchanged, continue with modifications of the protocol and/or the consent form to protect participant safety, or terminate the study. The study may be stopped if there are untoward and concerning levels of AE or SAE outcomes attributable to CBD or study participation. If the DSMB finds it is likely that CBD is contributing to negative outcomes, they will consider solutions including protocol changes or potentially stopping the study.

### 20.3.8 Multiple Comparison/Multiplicity

Because our primary outcomes are safety data, in which we hypothesize a null difference between treatment groups, we will not employ a correction for Type I error/alpha inflation.

### 20.3.9 **Tabulation of Individual Response Data**

Aside from AEs/SAEs, individual response data will not be presented.

### 20.3.10 Exploratory Analyses

### For Exploratory Hypothesis 1, relationship between PTSD/subthreshold PTSD and AUD symptom change

Symptom onset is defined to be the first week in which the patient has 50% reduction in the number of drinks per day for the primary alcohol outcome and a 30% reduction in the Total Score of the PCL-5 that is sustained for at least two weeks. Onset of a positive clinical outcome will be described by a "cure model." The form of a cure model is H(t) = 1 - p + pS(t); where H(t) is the probability of onset at a time greater than t, p represents the probability of success and S(t) is the distribution of time to success, conditional on success occurring. The parameters will be estimated based both on Kaplan Meier methods and parametrically. The equality of the values of p for the two treatment arms will be tested using a nonparametric likelihood ratio test. For the parametric test, a logistic will be used to model p and a Weibull survival distribution will be used to model time to failure, S(t). Both allow the use of covariates. The comparison will be based on a likelihood ratio test and the median time to onset of S(t).

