## 3.2 Secondary Objectives

Secondary objectives of this study are as follows.

- To assess the effect of CBD upon plasma CBD and THC levels when administered to patients with AUD+PTSD/subthreshold PTSD. We predict that within-group plasma CBD levels will stabilize within one week, i.e. 45 minutes post-CBD dosing levels obtained after 1 week of treatment will not differ from those obtained after 4 weeks of treatment.
- 2) To contrast the effects of CBD to those of placebo on psychological and cognitive domains relevant to AUD and PTSD/subthreshold PTSD. Relative to placebo, we predict that CBD will improve self-report measures of craving, anxiety, mood, and self-efficacy, and improve cognitive function. We will also specifically target the domain of traumatic stress induced craving using a human laboratory task. We predict that relative to placebo, CBD will lead to a greater attenuation in subjective traumatic stress and alcohol cue-induced craving and accompanying physiological stress response.
- 3) To assess the effect of CBD on plasma anandamide levels. We will contrast levels of plasma anandamide between samples taken at baseline and after CBD treatment, and between samples taken at predicted preand 45 minutes post-dosing CBD levels. We predict that relative to placebo, CBD will lead to an increase in plasma anandamide between these time points.
- 4) To assess the temporal relationship between the onset in reduction of PTSD symptoms and the onset in reduction of AUD symptoms. We predict that a reduction in PTSD symptoms will precede a reduction in

Exploratory Aim 1: To examine voicemarkers as a function of a patient's AUD and PTSD status and to develop assessment models that use lexical and prosodic features to classify a patient's AUD and PTSD status.

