#### **PTSD-related measures**

The PCL-5 will be administered at baseline, weeks 2, 4, 6 and 7. In addition to the PCL-5 score (primary PTSD endpoint), childhood trauma (child abuse and neglect) will be assessed at baseline using the self-report Childhood Trauma Questionnaire (CTQ) (28 item).

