#### 7.1.7 **PTSD-related measures:**

PTSD symptoms will be assessed with the PTSD checklist for the DSM-5 (PCL-5) [96]. Baseline PTSD symptoms will be defined as the total PCL-5 score at baseline. The primary PTSD outcome is the total score of the PCL-5 for each week administered. PTSD symptoms will be assessed before CBD or placebo treatment (baseline), at weeks 2, 4 and 6 of treatment, and one week after the completion of treatment (week 7).

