## 20.2 Statistical Hypotheses

Hypothesis 1a Safety and tolerability: CBD will be safe and well tolerated and will not lead to increased plasma THC. No clinically significant cognitive or motoric impairments, CBD-related serious adverse events, persisting adverse effects or treatment associated increases in plasma THC will be observed.

Hypothesis 1b: Alcohol use. Relative to the placebo-treated group, CBD-treated participants will have fewer drinks per day during the 6 weeks of treatment with CBD vs placebo.

Hypothesis 2: PTSD symptoms. Relative to the placebo-treated group, CBD-treated participants will lower PTSD symptoms during the 6 weeks of treatment with CBD vsplacebo.

Hypothesis 3a: Mechanism, traumatic stress-induced craving: Relative to placebo, CBD will be associated with a greater reduction between baseline and end of treatment in trauma induced alcohol craving, negative emotion, and psychophysiological arousal in response to the task.

Hypothesis 3b: Mechanism, AUD and PTSD related measures and cognition: Relative to placebo, CBD will improve self-report measures of craving, anxiety, mood, self-efficacy and cognitive performance.

Hypothesis 3c: Mechanism, anandamide: Relative to placebo, CBD will be associated with a greater increase

Hypothesis 4: CBD plasma levels. Within-group plasma CBD levels will stabilize within one week, i.e. 45 minutes post-CBD dosing levels obtained after 1 week of treatment will not differ from those obtained after 4 weeks of treatment at each dose.

Exploratory Hypothesis 1: Relationship between effects on PTSD symptoms and alcohol use. The onset of reduction in PTSD symptoms will precede the onset of reduction in alcohol use.

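### The analysis headed for the hypothesis that PTSD improvement precedes alcohol improvement tests response probability between arms; no stated step compares the two onset times

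*Combined protocol and SAP*

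**What the plan says.** Section 20.2 states Exploratory Hypothesis 1 as: "The onset of reduction in PTSD symptoms will precede the onset of reduction in alcohol use". Section 3.2 lists the same question as secondary objective 4: "To assess the temporal relationship between the onset in reduction of PTSD symptoms and the onset in reduction of AUD symptoms". The prediction attached to that objective is cut off in the text available to me, so I rely on Section 20.2 for the direction.

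Section 20.3.10 is headed as the analysis of this hypothesis. It does four things.

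- It defines onset: "Symptom onset is defined to be the first week in which the patient has 50% reduction in the number of drinks per day" for the alcohol outcome, "and a 30% reduction in the Total Score of the PCL-5 that is sustained for at least two weeks".
- It sets up a cure model, H(t) = 1 − p + pS(t), where p is the probability of success and S(t) describes time to success among those who succeed.
- It names one contrast: "The equality of the values of p for the two treatment arms will be tested using a nonparametric likelihood ratio test".
- It closes with a further step whose object is not given ("The comparison will be based on a likelihood ratio test and the median time to onset of S(t").

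On timing, Section 4.2.2 says "The PCL-5 will be administered at baseline, weeks 2, 4, 6 and 7" and Section 7.1.7 agrees: "PTSD symptoms will be assessed before CBD or placebo treatment (baseline), at weeks 2, 4 and 6 of treatment", plus week 7. Sections 2.3 and 4.1 instead describe weekly assessment of both drinking and PTSD outcomes. Section 20.1 says a formal SAP is still to be developed before database lock and unblinding.

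**The concern.** The hypothesis compares two outcomes, PTSD symptoms and drinking, on when each begins to improve. It is not a statement about CBD against placebo. The only contrast that the analysis names is CBD against placebo, on whether participants respond at all.

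A SAP that carried Section 20.3.10 forward unchanged would report a response-rate comparison under the heading of an order hypothesis. If order were instead read later from recorded onset weeks, the answer would depend partly on dating, threshold and sustain rules that had not been fixed in advance.

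**Working it through.** No figure in the plan needs reproducing here. The check sets the hypothesis beside the analysis and then asks what the recording schedule and the thresholds can show.

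**1. Does the test of p bear on order?** There are two readings of the onset sentence.

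- *One joint event* (both reductions required). Each participant has a single onset time, the later of the two. Neither p nor S(t) can then say which symptom came first.
- *Two separate events.* With complete follow-up, take every participant who has both onsets and swap the two times. Each outcome's p is unchanged in each arm, while the order is reversed in every untied case. The test of p therefore cannot distinguish the two orders.

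**2. Would medians by outcome do it?** If the closing sentence means a median for each outcome, that describes order at group level only. A constructed example with five participants: PTSD onset in weeks 2, 2, 2, 6, 6 and alcohol onset in weeks 2, 2, 4, 4, 4. The medians are 2 and 4, suggesting that PTSD leads. Participant by participant, PTSD is first in 1, alcohol is first in 2, and 2 are tied.

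**3. What can the schedule show?** Idealised inputs: true onset in weeks 1 to 6, each recorded at the next assessment, with no visit window and no sustain rule. Entries for a one-week lead count the pairs, out of 5, in which that lead is seen.

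| PCL-5 / drinks dated at | Simultaneous onset (6 cases) | PTSD leads by 1 week | Alcohol leads by 1 week |
|---|---|---|---|
| 2, 4, 6 / weekly | 3 tied, 3 alcohol-first | 2 of 5 | 5 of 5 |
| 2, 4, 6 / 1, 2, 4, 6 | 5 tied, 1 alcohol-first | 2 of 5 | 3 of 5 |
| Both weekly | 6 tied | 5 of 5 | 5 of 5 |
| Both 2, 4, 6 | 6 tied | 2 of 5 | 2 of 5 |

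The first row is the better-grounded reading of the detailed schedule, because drinks come from the Time Line Follow Back (Section 4.2.1) and several drinking endpoints are defined by week (Section 4.2.2). The second row takes the visits at which Section 7.3.3 lists alcohol use; the calls at weeks 3 and 5 do not list it. The third row follows Sections 2.3 and 4.1.

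**4. Do the thresholds themselves create order?** Suppose both outcomes fall together by 10% of baseline per week from week 0. PCL-5 reaches 30% at week 3 and is recorded at week 4. Drinks reach 50% at week 5 and are recorded at week 6. The result is PTSD-first although neither led.

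More generally, for a linear fall starting at week s and reaching a total relative drop D at week 6, threshold θ is crossed at t = s + (6 − s)θ/D. I simulated this with s uniform on 0 to 4 and D uniform on 30% to 100%, identical for both outcomes, on a shared 2, 4, 6 grid. Among participants with both onsets, 48% were PTSD-first, 0% alcohol-first and 52% tied. Every untied participant supports the hypothesis with no true order. With one common θ the two crossing times coincide and all are tied.

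**5. How precise could an order comparison be?** Assume independent response at rate r for each outcome and onset spread evenly over the shared grid, so that one third of both-onset cases tie.

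- r = 30%: 48 × 0.30² = 4.3 with both onsets, × 2/3 = 2.9 untied.
- r = 50%: 48 × 0.50² = 12, × 2/3 = 8 untied.
- r = 70%: 48 × 0.70² = 23.5, × 2/3 = 15.7 untied.

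These are before dropout and before any sustain rule, both of which lower them; positively correlated response would raise them. The exact 95% interval for 6 PTSD-first of 8 is 0.35 to 0.97.

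**The case against.** The strongest reply is that the section is about the relationship between the two symptom courses and gives each outcome its own threshold. Fitted once per outcome, the cure model yields a median onset time for each, and Section 20.2 does not say that order must hold within a participant. On that reading, the two medians would describe a group-level claim. This stands, and it is why a reader should not infer that the planned model could never address the hypothesis. What remains is that the text does not say the medians are to be compared between outcomes, and the only contrast named before that sentence is between arms.

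A reader might also infer from the schedule that the trial is biased toward finding alcohol first. The documents do not support a net direction. The PCL-5 schedule is itself in conflict, the visits carry windows of 5 days either way, the on-treatment PCL-5 recall period is not stated, and the unequal thresholds push the other way, toward PTSD-first.

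Finally, this is an exploratory question in a pilot focused on effect sizes (Section 20.3.1), with a SAP to come. That limits the consequence and makes the correction cheap, but it does not supply the missing comparison. Nor is the status settled: Section 3.2 lists the objective as secondary.

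**Conclusion.** The point holds. As written, the test headed for the order hypothesis carries no information on order, and the comparison that might address it has no stated object or estimand. This follows from the text and needs no numerical assumption.

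The dating and threshold findings are secondary and idealised. The 3 of 6 and 2 of 5 figures assume exact visit weeks and no sustain rule. The 48% figure assumes gradual, simultaneous, equal relative declines. They show that rules not yet fixed could change the answer, not that a particular bias will occur.

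The correction should be made before the SAP is finalised. It does not touch the primary drinking, PCL-5 or safety analyses.

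**What to change.** 1. Define two separate onset times per participant, one for drinks per day and one for PCL-5, and state whether the estimand is within-participant or group-level.
2. Reconcile Sections 2.3 and 4.1 with Sections 4.2.2 and 7.1.7 on the PCL-5 schedule. Date both onsets on a common grid (the PCL-5 visits, with a matched Time Line Follow Back window) or treat both as interval-censored. Apply one sustain rule to both. State how a week-6 PCL-5 onset is handled, since only week 7 follows it for that scale, whereas alcohol use is also recorded at week 9 (Section 7.3.4).
3. Add a stated comparison of PTSD onset with alcohol onset: counts of PTSD-first, alcohol-first, tied, PTSD-only, alcohol-only and neither, overall and by arm, with an exact confidence interval for the proportion PTSD-first among untied participants. Label it descriptive.
4. Report the same comparison with one relative-reduction threshold for both outcomes, and do not read the 30%/50% result alone as evidence of order.
5. Keep the cure model and the between-arm test of p as a description of response by arm, not as the test of order.
6. Label the objective consistently as secondary or exploratory.

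The cost is SAP wording and a reconciled schedule; the drinking and PCL-5 assessments it uses are already planned. The price is coarser alcohol timing, more ties and low precision, to a degree that depends on response rates and the sustain rule.

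### For PCL-5 onset, the cure-model fraction p and the median of S(t) in section 20.3.10 are not identified, so the planned comparison of p either has no power or compares onset by week 4

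*Combined protocol and SAP*

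**What the plan says.** Section 20.3.10 defines onset for drinking as the "first week in which the patient has 50% reduction in the number of drinks per day" and for PTSD as "a 30% reduction in the Total Score of the PCL-5 that is sustained for at least two weeks". The two criteria are joined by *and*, so the text can be read as two separate events or as one composite event.

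The model is H(t) = 1 − p + pS(t), where p is the probability of success and S(t) the distribution of time to success among those who succeed. On the comparison of arms the section says: "The equality of the values of p for the two treatment arms will be tested using a nonparametric likelihood ratio test". A parametric version uses a logistic model for p and a Weibull for S(t), and the median of S(t) is also compared. The section does not say whether S(t) is shared between arms, when follow-up for onset ends, or how an onset first seen at week 6 would be confirmed.

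On timing, section 4.2.2 (PTSD-related measures) says: "The PCL-5 will be administered at baseline, weeks 2, 4, 6 and 7". Section 7.1.7 and the visit lists in 7.3 agree. Alcohol use, by contrast, is also recorded at the week-9 call (section 7.3.4), where no PTSD measure is listed.

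**The concern.** A cure model separates how many succeed from how fast they succeed only if follow-up is long enough for the onset curve to flatten. With PCL-5 onset confirmable at two visits, no plateau can be seen. A difference in speed can then pass for a difference in p, or a difference in p can be absorbed entirely by the fitted timing.

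At stake is the interpretation. A significant result could be reported as CBD raising the probability of success when it only brought onset forward. A null result from the parametric version could be reported as no difference in success when the data could not have shown one. Section 20.3.1 makes effect sizes and response rates the main focus, and section 20.4 says that they are to inform later confirmatory trials, so a mislabelled response probability would carry forward.

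**Working it through.** The protocol gives no power, onset rate or onset speed for this analysis, so there is no figure of its own to reproduce. The power figure in section 20.4 is for a t test of means and does not enter here.

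**Inputs from the protocol.** 30 CBD and 18 placebo (20.5.1); two-sided 0.05 without multiplicity adjustment (20.3.1); PCL-5 at weeks 2, 4, 6 and 7; drinking recorded to week 9.

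**Assumptions.** No dropout, nominal visit dates, p = 0.70 in both arms, Weibull shape 1.3, and a range of median onset times with CBD the faster arm.

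**Step 1: confirmable PCL-5 onsets.** Week 2 is confirmed by week 4, and week 4 by week 6. Week 6 has only week 7 after it, which is one week. Two onset times remain.

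**Step 2: parameters against data.** Write F(t) = p[1 − exp(−(t/λ)^k)]. Each arm gives F(2) and F(4); the unknowns are p, k and λ. For any p above F(4), put A = −ln(1 − F(2)/p) and B = −ln(1 − F(4)/p). Then k = ln(B/A)/ln 2 and λ = 2/A^(1/k) reproduce both values exactly. With F(2) = 0.3 and F(4) = 0.5:

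| p | A | B | shape k | median of S(t), weeks |
|---|---|---|---|---|
| 0.5001 | 0.916 | 8.517 | 3.22 | 1.83 |
| 0.6 | 0.693 | 1.792 | 1.37 | 2.00 |
| 0.8 | 0.470 | 0.981 | 1.06 | 2.88 |
| 1.0 | 0.357 | 0.693 | 0.96 | 4.00 |

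The same data fit any p from 0.5 to 1, with medians from 1.8 to 4.0 weeks.

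**Step 3: Weibull fitted by arm.** Any common p above both arms' F(4) fits both arms exactly, so the likelihood ratio statistic for equal p is zero apart from boundary cases. In simulation (1000 runs per scenario) this test rejected in 0.0 to 0.5% of runs, and in 0% for p = 0.3 v 0.7 with 20 times the sample. Accepting week 7 as confirmation of a week-6 onset gives 1 to 14% power for the alternatives tried.

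**Step 4: Kaplan-Meier plateau test.** Without dropout this is a binomial likelihood ratio test of onset by the last confirmable week, rejecting above 3.841. With median m, F(t) = 0.70[1 − exp(−ln 2 · (t/m)^1.3)]; for example, m = 4 gives F(4) = 0.70 × 0.5 = 0.35. Summing binomial probabilities over all outcomes with n = 30 and 18:

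| Median onset, CBD v placebo (weeks) | Onset by week 4 | Rejects | Onset by week 8 | Rejects |
|---|---|---|---|---|
| 2 v 2 | 0.57 v 0.57 | about 5% | 0.69 v 0.69 | about 5% |
| 2 v 3 | 0.57 v 0.44 | 15% | 0.69 v 0.64 | 7% |
| 1.5 v 4 | 0.64 v 0.35 | 53% | 0.70 v 0.57 | 15% |
| 2 v 6 | 0.57 v 0.24 | 67% | 0.69 v 0.44 | 41% |

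The week-4 columns apply to PCL-5 and the week-8 columns to drinking analysed separately. True p is equal in every row.

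**Step 5: shared Weibull.** Sharing S(t) identifies the ratio of the two p values but neither their level nor the median, and it assumes equal speed. On the PCL-5 visits it behaves like the plateau test. With exponential onset both reject equal p in 19% of runs (p = 0.6, medians 4 v 2 weeks), 36% (0.6, 6 v 2) and 59% (0.8, 6 v 2).

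**Step 6: drinking, onset counted through week 8.** With exponential onset and unequal speed, the plateau test rejects equal p in 14 to 48% of runs, and the by-arm Weibull has 11 to 20% power for p = 0.3 v 0.7. With quick, completed onset (shape 2, medians 1 to 3 weeks), the plateau test holds 5 to 6% and the by-arm Weibull has 52 to 58% power. The ceiling, if eventual success were fully observed, is about 80%.

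**The case against.** *The protocol says probability of success, not eventual success.* On that reading the nonparametric test does test its null, and 53% is power for a real difference by week 4. But in H(t) = 1 − p + pS(t), S(t) falls to zero, so 1 − p is the fraction that never succeeds. If success by a fixed week is meant, the section needs to say so.

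*The fix nearly repeats the planned test.* Largely true. Without dropout, the plateau test and a two-sample comparison of onset by week 4 are almost the same calculation. For that test the gain is a correct label, an interval and a stated horizon. The unidentified cure fraction and median are the parts that go.

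*PCL-5 data may be denser.* Sections 2.3 and 4.1 describe weekly PTSD assessment, in conflict with 4.2.2, 7.1.7 and the visit lists. I followed the visit lists, where weeks 1, 3 and 5 carry no PTSD measure. The ±5-day windows could put some week-6 and week-7 visits 14 or more days apart (at most 7 + 10 = 17), but the protocol does not rely on this.

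*Drinking is different.* This stands. A reader might infer that p is unidentified for drinking too, or that the whole onset analysis is powerless. The protocol does not support either: alcohol use is recorded to week 9, section 20.3.10 sets no earlier cut-off, and the two-week rule attaches grammatically to the PCL-5. The near-zero power also belongs only to a Weibull fitted by arm, which the section neither specifies nor excludes.

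*It is exploratory.* Also fair. Section 20.3.1 expects little significance, and 20.1 leaves a formal SAP to be written before lock and unblinding.

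**Conclusion.** The point holds for PCL-5 onset, and for the whole analysis if onset is one composite event, because the PCL-5 visits then set the window. Non-identification of p and of the median of S(t) is algebra and rests only on the visit schedule and the two-week rule. The rejection rates of 15%, 53% and 67% rest on the assumed p, shape and medians, and on no dropout. They need a true difference in speed; with equal speed the plateau test keeps about 5%.

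For drinking analysed separately, identification is unsupported rather than ruled out. The same scenarios give 7%, 15% and 41% through week 8, and quick, completed onset would largely remove the problem. The consequence is modest: an exploratory result that could be described wrongly.

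**What to change.** In section 20.3.10, or in the SAP promised in 20.1:

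- Define onset separately for the two outcomes, or state that it is composite. Say whether the two-week rule applies to drinking and how a week-6 PCL-5 onset is treated.
- For PCL-5 and any composite, drop the logistic/Weibull cure fraction and the median of S(t). State the estimand as the proportion with sustained onset by week 4, the last confirmable week; compare arms by risk difference with 95% CI, and do not call it eventual success.
- For drinking, use all Timeline Follow-Back data to week 9, fix the horizon in advance and report cumulative onset by that week. Interpret p only if the curves plateau in both arms, and state whether S(t) is shared.
- Keep interval-censored onset curves for both outcomes, so that the order of PTSD and alcohol onset in Exploratory Hypothesis 1 can still be described.

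The cost is wording only: no visit, measurement or sample-size change. What is lost is a statement about eventual PCL-5 responders, which this follow-up cannot support. Power stays limited by n = 48: with 30 v 18, a comparison by a fixed week has power 0.27 for 40% v 60%, 0.52 for 30% v 60% and 0.79 for 30% v 70%. The interval should therefore carry the report.
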